10.1. Software for Data Capture

The study personnel will enter the study data into a REDCap spreadsheet. REDCap is a HiPAA-compliant data capture system provided by the NC TraCS Institute at UNC. The data system includes password protection and internal quality checks, such as automatic range checks, to identify data that appear inconsistent, incomplete, or inaccurate. Study data will be entered directly from the medical chart, Rs-fMRI report, Core Disease CRF (appendix G) and one of the NSICU Post-Discharge clinics forms (appendix H, I, J, K, L).

10.2. Responsibilities for Data Capture and Database Management

Data collection is the responsibility of the research staff at the site under the supervision of the PI. The PI is responsible for ensuring the accuracy, completeness, legibility, and timeliness of the data reported. The study

coordinator or the coinvestigators that performs the consent interview will be responsible of interrogating the premorbid Barthel Index, initial filling up the Core Disease CRF and give it to the research staff to collect those data into the database.

All source documents will be completed in a neat, legible manner to ensure accurate interpretation of data. Data recorded in the electronic case report form (eCRF) derived from source documents should be consistent with the data recorded on the source documents.

Clinical data including adverse events (AEs), concomitant medications, and expected adverse reactions data) and research test data will be entered into **REDCap**, a HiPAA compliant data capture system provided by the **NC Tracs**. The data system includes password protection and internal quality checks, such as automatic range checks, to identify data that appear inconsistent, incomplete, or inaccurate. Clinical data will be entered directly from the source documents.

10.3. Study Records Retention

Study documents should be retained until at least 5 years have elapsed since the formal discontinuation of clinical development of the study intervention. These documents should be retained for a longer period, however, if required by local regulations. No records will be destroyed without the written consent of the UNC Neurology Department and the Director of the UNC Clinical Resting State fMRI service.

11. Collection and Management of Tissue Specimens

11.1. Use in Current and Future Studies

If one of the combined doses administered is phenobarbital, on Day 2 the MD a blood sample will be collected for phenobarbital serum level (UNC Hospitals Test ID LAB30) to adjust the phenobarbital dose, aiming for a serum concentration of 40mcg/ml. The specimen collection will be ordered by the research team.

11.2. Sample Preparation

For the Phenobarbital serum levels measure 2 mL of blood are withdrawn by corresponding ICU nurse personnel from a central or arterial line using aseptic technic. If no adequate lines in place are available, the blood is acquired by phlebotomy performed by lab personnel. Immediately after withdrawal the blood is stored in a royal blue top tube or plain red top tube (no gel). After proper labeling with the research subjects MRN, it is transported at room temperature to the Core Laboratory for spin within 4 hours and further processing.

11.3. Record Keeping and Monitoring

The results will be informed and kept as regular tests done for clinical purposes. The results will not be stored by the research team, but will be used for safety purposes to provide a one time feedback to the care team in order to adjust dosing if deemed necessary.

11.4. Storage and Security

The sample will be stored, processed and discarded according to the usual standard procedures of UNC Health Hem Onc Laboratory. It will not be kept for future research purposes.

12. Safety Monitoring and Management

12.1. Risk / Benefit Assessment

No psychological, social, legal or economic risks are anticipated with the study for the patients or the community.

Main Potential Risks (Based on frequency and severity):

Potential Risks: Physical risk of accidents during transportation to MRI scanner and scanning time.

This includes but is not limited to intravenous access displacements, falls, contusions, mechanical ventilation decoupling or displacement of medical devices.

Frequency: Uncommon to Rare.

Severity: Mild to severe, being rare the severe ones.

This risk is reduced by transport monitoring and care by a fellow physician, one respiratory therapist and two nurses. Enough clinical stability to transport to MRI scan by care team criteria is required.

Potential Benefits: For the individual participant the information acquired from the MRI scan can help guide treatment and can also provide useful information for neuro-prognostication. It also is the exam that defines the classification into intervention and no intervention groups.

Phenobarbital

Potential Risks: Physical risk of unknown hypersensitivity or unexpected reaction.

This includes non-dose dependent reactions like serious dermatologic reactions or drug reactions with eosinophilia and systemic symptoms (DRESS)/multiorgan hypersensitivity, and dose dependent adverse effects presented while on the adequate range for age and weight like prolongation of QT.

Electrocardiographic monitoring is standard of care for the ICU patients, which improves the safety of this drug use. Patients with porphyria will not be allocated to treatment with phenobarbital. Sedation or ventilatory depression by Phenobarbital are not relevant risks in this study because it would only be administered to patients that require ventilatory support. The risk of abuse and dependence on Phenobarbital is associated with use for prolonged periods of time so it also is not going to be considered.

Frequency of dermatologic reactions or hypersensitivity: Rare.

Severity: Mild to severe, being rare the severe ones.

Source: FDA labeling (appendix E)

Potential Benefits: As the rationale of this study explains, this medication could improve the control over epileptogenic activity, improving normal brain connectivity and clinical outcome, and in the context of the present study, will be administered to patients with abnormal resting state networks that are suspected of having an epileptogenic correlate. The available alternative options in the current clinical practice for MSABI patients with persistent consciousness compromise, risk of epileptogenic activity, and no electroencephalographic indication of increasing the ASM in their treatments are:

1. Wait for the clinical evolution assuming there is no additional benefit for stronger ASM and consciousness compromise is not related to the epileptogenic activity.
2. Increase the ASM regimen strength to test the hypothesis that epileptogenic activity might be involved in the consciousness compromise.

Levetiracetam

Potential Risks: Physical risk of unknown hyper sensibility or unexpected reaction.

This includes non-dose dependent reactions like serious dermatologic reactions or drug reactions with eosinophilia and systemic symptoms (DRESS)/multiorgan hypersensitivity, and dose dependent adverse effects presented while on adequate range for age and weight like hematologic abnormalities.

Frequency of dermatologic reactions or hypersensitivity: Rare.

Severity: Mild to severe, being rare the severe ones.

Source: FDA labeling (appendix D)

Potential Benefits: As the rationale of this study explains, this medication could improve the control over epileptogenic activity, improving normal brain connectivity and clinical outcome, and in the context of the present study, will be administered to patients with abnormal resting state networks that are suspected of having an epileptogenic correlate. The available alternative options in the current clinical practice for MSABI patients with persistent consciousness compromise, risk of epileptogenic activity, and no electroencephalographic indication of increasing the ASM in their treatments are:

1. Wait for the clinical evolution assuming there is no additional benefit for stronger ASM and consciousness compromise is not related to the epileptogenic activity.
2. Increase the ASM regimen strength to test the hypothesis that epileptogenic activity might be involved in the consciousness compromise.

Lacosamide

Potential Risks: Physical risk of unknown hyper sensibility or unexpected reaction.

This includes non-dose dependent reactions like serious dermatologic reactions or drug reactions with eosinophilia and systemic symptoms (DRESS)/multiorgan hypersensitivity, and dose dependent adverse effects presented while the on adequate range for age and weight like cardiac rhythm and conduction abnormalities.

Frequency of dermatologic reactions or hypersensitivity: Rare.

Severity: Mild to severe, being rare the severe ones.

Source: FDA labeling (appendix C)

Potential Benefits: As the rationale of this study explains, this medication could improve the control over epileptogenic activity, improving normal brain connectivity and clinical outcome, and in the context of the present study, will be administered to patients with abnormal resting state networks that are suspected of having an epileptogenic correlate. The available alternative options in the current clinical practice for MSABI patients with persistent consciousness compromise, risk of epileptogenic activity, and no electroencephalographic indication of increasing the ASM in their treatments are:

1. Wait for the clinical evolution assuming there is no additional benefit for stronger ASM and consciousness compromise is not related to the epileptogenic activity.
2. Increase the ASM regimen strength to test the hypothesis that epileptogenic activity might be involved in the consciousness compromise.

Valproate

Potential Risks: Physical risk of unknown hyper sensibility or unexpected reaction.

This includes non-dose dependent reactions like serious dermatologic reactions or drug reactions with eosinophilia and systemic symptoms (DRESS)/multiorgan hypersensitivity, and dose dependent adverse effects presented while on the adequate range for age and weight like Hepatotoxicity and pancreatitis.

Frequency of dermatologic reactions or hypersensitivity: Rare.

Severity: Mild to severe, being rare the severe ones.

Source: FDA labeling (appendix F)

Potential Benefits: As the rationale of this study explains, this medication could improve the control over epileptogenic activity, improving normal brain connectivity and clinical outcome, and in the context of the present study, will be administered to patients with abnormal resting state networks that are suspected of having an epileptogenic correlate. The available alternative options in the current clinical practice for MSABI patients with persistent consciousness compromise, risk of epileptogenic activity, and no electroencephalographic indication of increasing the ASM in their treatments are:

1. Wait for the clinical evolution assuming there is no additional benefit for stronger ASM and consciousness compromise is not related to the epileptogenic activity.
2. Increase the ASM regimen strength to test the hypothesis that epileptogenic activity might be involved in the consciousness compromise.

Fosphenytoin

Potential Risks: Physical risk of unknown hyper sensibility or unexpected reaction.

This includes non-dose dependent reactions like serious dermatologic reactions or drug reactions with eosinophilia systemic symptoms (DRESS)/multiorgan hypersensitivity, and administration rate dependent adverse effects like cardiac arrhythmias. Hematologic complications and local toxicity have been reported. It will not be administered in patients with porphyria.

Frequency of dermatologic reactions or hypersensitivity: Rare.

Severity: Mild to severe, being rare the severe ones.

Frequency of cardiac arrhythmia: rare at infusion rates of 150 mg phenytoin sodium equivalents (PE) per minute in adults and 2 mg PE/kg/min (or 150 mg PE/min, whichever is slower) in pediatric patients.

Severity: Can be severe.

Source: FDA labeling (appendix B)

Potential Benefits: As the rationale of this study explains, this medication could improve the control over epileptogenic activity, improving normal brain connectivity and clinical outcome, and in the context of the present study, will be administered to patients with abnormal resting state networks that are suspected of having an epileptogenic correlate. The available alternative options in the current clinical practice for MSABI patients with persistent consciousness compromise, risk of epileptogenic activity, and no electroencephalographic indication of increasing the ASM in their treatments are:

1. Wait for the clinical evolution assuming there is no additional benefit for stronger ASM and consciousness compromise is not related to the epileptogenic activity.
2. Increase the ASM regimen strength to test the hypothesis that epileptogenic activity might be involved in the consciousness compromise.

The comprehensive mention of additional recognized AE related to the ASM listed on the protocol is included under section 12.3, “Grading the Severity of Adverse Events and Events of ‘Special Interest’”.

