4.3. Measurement Design

Table 2. Variables of interest: their occasions of evaluation, their uses for the aims, their roles in the study

Variables within Domains	Scale ¹	Occasions ²	Aims ³	Main Roles
Identifiers				
Participant's unique ID	nominal	all	all	identifier

Intervention	categorical	E	All, except aim 2	intervention
Clinical Health Profile				
Spontaneous ventilation	Binary	E, 2	Aim 1	Exploratory uses
Glasgow Coma Scale (GCS)	Ordinal 3-15	S, E, 2	--	Screening
weight	kg	E	--	dosing
height	cm	E	--	dosing
body mass index (BMI)	kg/cm ²	E	--	dosing
body surface area (BSA)	kg/m ²	E	--	dosing
Supratentorial decompressive craniectomy	Binary	S, E, 2	--	Exploratory uses
age	decimal yrs	S	--	screening
sex	categorical	S	--	Exploratory uses
Pre-MSABI BIS (appendix a)	Ordinal 0-100	S	--	screening
Medical Records				
Presumed etiologies of disorder of consciousness	Categorical	S	--	screening
co-morbidities list	nominal	S	--	screening
Clinical tests				
2HELP2B Score	Ordinal 0-7	S	--	Exploratory uses
pre-intervention EEG status (EEG monitoring Seizures)	Binary	E	All	classification
Research tests				
SzNET presence	Binary	E	All	Classification and primary outcome
Total Volume (TV)	continuous	2	Aim 1a	primary outcome
Total Volume Reduction (TVR)	continuous	2	Aim 1a, 3, 4	primary outcome
Power Spectrum (PS)	continuous	2	Aim 1b	primary outcome
Power Spectrum Improvement (PSI)	continuous	2	Aim 1a, 3, 4	primary outcome
Typical RSN improvement	Binary	2	Aim 4	Secondary outcome
EEG improvement	Binary	2	Aim 3	Secondary outcome
Protocol Time Frames				
Days of antiseizure medication	Days (discrete)	2	-	Confounder
Time from MSABI to rs-fMRI#1 (days)	Days (discrete)	2	-	Confounder
Time from MSABI to rs-fMRI#2 (days)	Days (discrete)	2	-	Confounder
Time from MSABI to treatment protocol start (days)	Days (discrete)	2	-	Confounder
Time from enrollment to rs-fMRI#1	Days (discrete)	2	-	Secondary outcome
Questionnaires/survey instruments⁴				
Anxiety: PROMIS Emotional Distress—Anxiety—Short Form (appendix H)	Ordinal 7-35	3	Aim 5	Exploratory outcome

Depression: Neurological Disorders Depression Inventory for Epilepsy (NNDI-E) (appendix I)	Ordinal 6-24	3	Aim 5	Exploratory outcome
Quality of Life: QOLIE-10-P (appendix J)	Ordinal 1-10	3	Aim 5	Exploratory outcome
Telephonic Montreal Cognitive Assessment (appendix K)	Ordinal 0-15	3	Aim 5	Exploratory outcome
ASM toxicity: Liverpool adverse event profile test (appendix L)	Ordinal 19-76	3	Aim 5	Exploratory outcome

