 - Review adverse events
 - Review participant medical record to confirm which combined ASM was decided by the clinical care team and charge it into EPIC.
 - Document date and time of first intervention-related loading dose infusions.

Maintenance Dose (Up to 3 to 10 Days from loading dose start)

- **Research Team** will charge to EPIC the maintenance doses and verify ASM Administration.
 - The maintenance protocols must be administered for at least 72 hours from the start time of the loading dose infusion.
 - The MD can continue for up to 10 days while the second fMRI is trying to be scheduled and obtained.
 - The ASM can be continued beyond 10 days but would no longer be considered in the protocol-driven intervention phase.
 - The Post-Intervention assessment scans can be obtained, even if the participant remains on ASM beyond the maintenance dose period.
 - **To undergo any study indicated rs-fMRI, the participant should not have been diagnosed with vasospasm based on their most recent transcranial Doppler examination, conducted within the last 3 days.**
 - If one of the combined doses administered is phenobarbital
 - *On Day 2 of the MD:*
 - ♦ Specimen Collection (phenobarbital serum level UNC Hospitals Test ID LAB30) will be ordered by the research team.
 - ♦ The **research team** reconvenes the maintenance dosing with the **medical care team** to aim for a level of 40mcg/ml.
 - Review any AEs associated with ASM
 - Review Dropout data (if applicable)

- **Medical Care Team** will decide if the patient continues with the study's antiseizure medication regimens. In this case, they will continue to provide the medication, and the patient will be responsible for expenses.

Acquisition, storage and preparation: The present study does not employ experimental compounds, all the medications related to the study follow the same standard Storage rules of the medications regularly used at the ICUs of UNCH.

Administration: IV and enteral administration with infusion times and observation according to the internal protocols for each medication at the patient's corresponding ICU.

Rescue Procedures/Medications

- If emergent adjustments to the treatment plan are needed those will be decided by the care team.
- Administration of additional ASM to the study intervention is allowed as determined by the clinical team.

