7.2. Screening

Patients meeting eligibility criteria will be followed by the research personnel to check with the care team the time when the clinical condition of the patient is stable enough to be transported, and MRI scanned. The communication between the research team and the care team will be telephonic. Once the care team accepts and informs that the patient can be screened, the study personnel will check the compliance with inclusion/exclusion criteria listed, call the Patient's family or LAR to inform them about the study and will ask for verbal informed consent to screen the

patient. If the family agrees, the study personnel will schedule the screening/enrollment interview as soon as possible.

Prescreening Assessments Activities (days -90 to -1): The research team will only perform medical chart review of the patients that have an EEG requested.

- Assessing for an ordered clinical care EEG.
 - 2HELP2B Assessment reviewed from the baseline EEG.
 - Stratification of Pre-Screening EEG Data (retrieved from medical record review).
 - EEG(+): had a **presence** of electrographic seizure, electroclinical seizure or ictal-interictal continuum.
 - EEG(-): was **negative** for electrographic seizure, electroclinical seizure or ictal-interictal continuum.
- Medical chart review: Presumed etiologies of disorder of consciousness, Epilepsy antecedent, other comorbidities list, current spontaneous ventilation, height, weight, BMI, BSA, age, sex, pregnancy condition, supratentorial decompressive craniectomy, GCS score and current neurological responsiveness.
- Contacting care team to ask for clinical stability to MRI scan and authorization to contact the LAR.
 - Contacting the LAR to obtain verbal consent to administer the BIA.

Screening/enrollment interview (Day 0)

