7.3. Enrollment

Once informed consent is obtained and the patient is enrolled, the coordinator will double-check previous history of porphyria, allergies, and hypersensitivity to the potential ASM listed in the study to provide a list of the treatment protocols that could be used for the patient if allocated to intervention. On the same day, the study coordinator will schedule the rs-fMRI for the following days and inform the research and the care teams of the scheduled date. This date should be within three days at maximum, and the intervention allocation must be done within six days from enrollment. Considering those dates, the minimum and maximum times from MSABI to the first rs-fMRI are 4, and 48 days correspondingly. The minimum and maximum times from MSABI to the intervention are 5 and 51 days, correspondingly. The family will be told that all the rs-fMRI results will be provided and explained after the follow-up research tests, and no further instructions are needed.

Screening/enrollment interview Activities (Day 0)

- BIS assessment for score (>80) through interview with potential LAR.
- Written Informed Consent Obtained from LAR.

- Consent must be obtained within 90 days from the participant's MSABI.
- Confirming baseline variables are collected through medical chart review.
 - Supratentorial decompressive craniectomy, current GCS score, presence of spontaneous ventilation.
- Verify with the LAR about: porphyria, co-morbidities, medical implants or contraindications for MRI, allergies, and hypersensitivity to the potential ASM.
- Provide a list of the treatment ASMs recommended for this participant that could be used if allocated to intervention.
- Notify Clinical Team about participant enrollment.
 - Verify with study team about which 2 combined ASMs could be administered in case of allocation to treatment.
 1. Phenobarbital 20 mg/kg loading dose
 2. Levetiracetam 60mg/kg loading dose
 3. Lacosamide 10 mg/kg loading dose
 4. Valproate 30 mg/kg loading dose
 5. Fosphenyton 20 mg/kg loading dose

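### Section 12.1 dismisses sedation and ventilatory depression because phenobarbital goes only to patients who need ventilatory support, but no eligibility, loading or reload rule ensures that for GCS below 9

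*Combined protocol and SAP*

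**What the plan says.** Section 12.1 covers phenobarbital's risks in one paragraph. It first sets a limit for one group: "Patients with porphyria will not be allocated to treatment with phenobarbital". It then says that sedation and ventilatory depression "are not relevant risks in this study because it would only be administered to patients that require ventilatory support".

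Other sections are more cautious. Section 2.2 names ventilatory depression as the drug's main side effect of concern and calls it less relevant here because many of these patients already have a secure airway. Section 4.1 expects patients with severe injury to be intubated during the study period. It bars phenobarbital at GCS 9 to 12 because those patients are at lower risk and may not need ventilatory support.

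Ventilation status is collected. Prescreening in 7.2 reviews "current spontaneous ventilation, height, weight, BMI, BSA, age, sex, pregnancy condition", and the Day 0 list in 7.3 confirms "current GCS score, presence of spontaneous ventilation". In Table 2 of section 4.3, "Spontaneous ventilation" is scheduled at enrollment and at the second scan, with an exploratory role.

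**The concern.** The dismissal in 12.1 rests on a factual claim about who receives the drug. If no rule makes the claim true, the risk assessment excludes something that the dosing text allows: a participant with GCS below 9 who is breathing without support and receives a full phenobarbital load.

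That matters because phenobarbital is in the first-line pair and is given as a 20 mg/kg intravenous load, with a possible reload. Participants cannot consent for themselves and include children, and section 5.3.1 classes the research as greater than minimal risk. The argument in 4.1 against needing an IND also relies on the intervention not significantly increasing risk. The stated basis for setting aside a named side effect should therefore match the procedures.

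**Working it through.** No power, rate or error calculation is involved. The check is whether any operative rule makes phenobarbital conditional on ventilatory support when GCS is below 9.

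1. **Eligibility (synopsis, 5.2).** Entry requires GCS below 13 and an ICU stay; 5.2.1 adds stability for MRI. The exclusions cover contraindications to the drugs and the treating physician's judgement that two of the five cannot be given. Neither list has an airway or ventilation criterion.
2. **Loading (synopsis, 4.1, section 6).** The load is 20 mg/kg intravenously, with a 1000 mg cap for children and no adult load cap stated. Phenobarbital plus levetiracetam is the first option. The section 6 branches depend on which listed drugs the participant already takes, not on ventilation.
3. **GCS 9 to 12 (4.1, section 6).** This is the only severity limit on phenobarbital. Need for ventilation is its reason, but GCS is its criterion. It does not reach an unventilated participant with GCS below 9.
4. **Reload (4.1, section 6, 11.3).** The serum level is measured on day 2, and a new load targets 40 mcg/ml. Section 6 also says the research team "reconvenes the maintenance dosing with the" care team, and 11.3 describes feedback of the level "in order to adjust dosing if deemed necessary". A reload therefore depends on the level and on clinical review. None of these texts mentions ventilation.
5. **Building the drug list (7.3).** The prose has the coordinator check "previous history of porphyria, allergies, and hypersensitivity to the potential ASM listed in the study to provide a list of the treatment protocols". The Day 0 activity list confirms spontaneous ventilation shortly before the recommended drugs are listed. The information is at hand, but no instruction links it to phenobarbital.
6. **Statements about ventilation (2.2, 4.1).** These are an estimate (many) and an expectation. Neither supports the word only in 12.1.

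Sedation has a further gap. Ventilatory support addresses breathing, not sedation. The tables in 12.3 list somnolence under levetiracetam and valproate, but the phenobarbital tables list no sedation term.

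**How many could be affected.** Planned treated participants: 11 + 11 = 22. Let k be the number of these with GCS 9 to 12, who are barred from phenobarbital. The affected number lies between 0 and 22 − k. The documents give neither k nor the share below GCS 9 without ventilatory support, so no point estimate is possible.

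**Age of the last scheduled ventilation reading at the load.** That reading is taken at enrollment, and section 6 requires treatment to start 1 to 6 days after enrollment. The reading is therefore 1 to 6 days old. The Table of Events agrees: 6 + 10 = 16 days for the end of the intervention phase and 6 + 13 = 19 days for follow-up tests.

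**The case against.** The strongest reply is that 12.1 is itself protocol text. Its sentence can be read as a restriction, standing beside the porphyria limit, which does not appear in the 4.1 dosing rules either. On that reading the condition exists but is stated only once. This is arguable, but the sentence is worded as a reason for dismissing a risk, not as an instruction. Porphyria also appears in the exclusion criteria and in the drug-list step of 7.3, where someone acting on the protocol would meet it. The ventilation condition appears in neither as a rule. Part of the reply stands: the GCS 9 to 12 bar does carry the ventilation rationale into procedures, though only by proxy.

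The second reply is that safeguards surround the drug. The care team may choose another pair if phenobarbital is unsuitable. ICU patients have airway and ventilation monitoring. Section 12.1 closes by sending the reader to 12.3, where the phenobarbital tables open with respiratory events graded 1 to 5. Grade 4 events end the intervention (7.8), serious events lead to withdrawal (12.2), and the FDA insert is among the consent materials (13.1.1). All of this stands as mitigation, but it is not the restriction that 12.1 claims.

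Four stronger readings are tempting, and the documents do not support them:

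- **Unventilated participants will be given phenobarbital.** The text permits it; nothing shows that it will happen.
- **Respiratory risk is left out of safety handling, or ventilation is ignored at enrollment.** Sections 12.3 and 7.3 show otherwise.
- **The ventilation reading could be 9 days old**, by adding the 3-day scan window to the 6-day scan-to-treatment range. The mandatory start within 6 days of enrollment and the Table of Events totals rule this out. The care team giving the load can in any case see current status.
- **The consent form repeats the 12.1 claim.** Its text is not in the available copy.

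**Conclusion.** The inconsistency holds in a narrow form. Section 12.1 says a group of recipients cannot exist, while the eligibility, loading and reload text allows it for GCS below 9. This is a minor to moderate safety-consistency fix. It does not show that the regimen is unsafe, and it does not affect the analysis of any aim.

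The number affected is unknown and may be zero. The conclusion assumes that the 12.1 sentence is a justification and not a dosing rule. If the sponsor intended it as a rule, the remaining defect is that the rule is missing from the sections that staff follow when dosing.

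**What to change.** Either of two changes resolves it.

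(a) Correct 12.1. List sedation and ventilatory depression as relevant, monitored phenobarbital risks, reduced because many or most recipients are ventilated and all are in an ICU. This costs one amended sentence and brings 12.1 into line with 2.2, 4.1 and 12.3.

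(b) Make 12.1 true. State in 4.1, section 6 and 7.3 that phenobarbital loads and reloads are given only to participants on ventilatory support at the time of dosing, and that others receive an already permitted pair such as levetiracetam plus lacosamide. This needs a re-check, at each load or reload, of a variable already collected. The downside is possibly fewer participants on the first-line pair and a more mixed set of regimens. No new regimen is needed, and section 4 already anticipates similar efficacy from the alternatives.

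Under either option, align the consent text if it repeats the 12.1 statement.
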